13.1.3 Analysis Populations

Safety set:	All subjects who received at least some portion of the contrast agents (Lumentin® 44, diluted Omnipaque® and Movprep®). Subjects will be included in the analysis according to the treatment actually received.
Full analysis (FA) set:	All correctly included and randomised subjects who received at least some portion of the contrast agents (Lumentin® 44, diluted Omnipaque® and Movprep®) and for whom a CT-scan has been performed. All subjects will be included in the group according to the intention based on the randomisation.
Per protocol (PP) set:	All subjects of the FA set who are compliant with the trial protocol, i.e., who do not experience any major protocol deviations.

All efficacy analyses will be performed for both the FA set and the PP set. The analysis of the primary efficacy parameter based on the PP set will be regarded as the primary analysis. The analyses on the FA set will be considered as sensitivity analyses.

All safety analyses will be based upon the Safety Set.

13.2 General Considerations

All statistical tests will be 2-sided and significance-values less than 5 % will be considered statistically significant even though adjustment for multiplicity will not be performed, unless otherwise stated. Confidence intervals will be two-sided at the 95% confidence level.

Continuous data will be summarised using descriptive statistics (N, mean, median, standard deviation, minimum and maximum). Categorical data will be summarised by frequency tables (numbers and percentages).

Unless otherwise stated, all analyses will be done on observed cases without any substitution of missing values.

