- a) No formal screening will be performed in the trial. However, since only one visit to the clinic is planned in this trial, all subjects will receive information regarding the trial prior to the clinic visit. Subjects will thus have time to consider participation and prepare questions, if needed.
- b) Also in case a subject is withdrawn after intake of the contrast agent the Early Termination form should be completed.
- c) Urine pregnancy test of all fertile females
- d) Blood sample (2 mL) will include Na, K, Ca, P in serum and will be taken prior to intake of contrast agents and post CT-scan.

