6.2 Secondary Objectives

- To describe and compare the ability of Lumentin® 44 to fill the bowel as compared to Movprep® and diluted Omnipaque®.
- To describe and assess how Lumentin® 44 influences reading of the abdominal CT-examination as compared to Movprep® and diluted Omnipaque® with respect to:
 - Diagnostics with particular regard to parenchymal organs, lymphatic system and tissue compartments beyond the gastrointestinal tract
- To investigate signs of degradation of Lumentin® 44 in terms of
 - Coalescence
 - Syneresis or drainage
- Describe and compare the ability to eat/drink for each of three contrast agents with respect to:
 - Taste
 - Smell
 - Consistency
 - Ability to swallow
 - Fullness
- Validity and repeatability of the primary endpoint
- To evaluate safety and tolerability after oral administration of each of three contrast agents

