7.2.3 Safety Variables

The safety parameters consist of:

- Especially solicited adverse events (AEs), i.e. stomach ache, burping, letting go of wind, Nausea and sensation of fullness
- Any treatment emerging adverse events
- Any treatment emerging adverse drug reactions (ADR)
- Safety laboratory evaluations (clinical chemistry)
- The reasons for withdrawal from the trial

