9 INVESTIGATIONAL PRODUCTS

9.1 Investigational products

9.1.1 Lumentin® 44

Lumentin® 44 Dispersion will be manufactured and released by Bioglan AB, [name], Sweden.

Table 1: Lumentin® 44 Dispersion

Ingredients	Lumentin® 44 Dispersion
	Concentration (g/100g)
Egg White Powder	1.93
Sodium dihydrogen phosphate dihydrate (NaH ₂ PO ₄ • 2H ₂ O) ¹	0.19
Dibasic potassium phosphate (K ₂ HPO ₄) ¹	0.63
Xanthan gum ¹	0.48
Flavour ²	0.24
Water, purified ¹	96.53

1) *Ph. Eur.: European Pharmacopoeia*

2) *The flavour mixture contains vanillin, Propylene Glycol (E1520) and water and belongs to a product range registered under a DMF in the US.*

Lumentin® 44 Foam

The final preparation of the investigational product, Lumentin® 44, will be performed at the clinic, see appendix 1, Lumentin® 44 dispersion whipping protocol

Lumentin® 44 contains the exact same ingredients as Lumentin® 44 Dispersion, see table 1, except for added air due to the whipping process.

9.1.2 *Diluted Omnipaque®*

Omnipaque® 240 mg I/mL is manufactured by GE Healthcare AS, [name], Norge.

Table 2: Omnipaque® 240 mg I/mL

Ingredients	Concentration (mg/mL)
Iohexol	518
Iodine equivalent	240
Tromethamine	1.21
Edetate calcium disodium	0.1
Hydrochloric acid	1
Sodium hydroxide	1

¹ For pH adjustment only

Diluted Omnipaque®

30 ml of Omnipaque® 240 mg I/mL will be mixed with 970 ml water.

The final preparation of the investigational product, diluted Omnipaque®, will be performed at the clinic.

9.1.3 *Movprep®*

Movprep® is distributed by Norgine BV, [name], The Netherlands.

Movprep® is distributed as two dose units, Unit A and Unit B.

Table 3: Movprep®

Ingredients	Content (g)
Unit A	-
- Macrogol 3550	100
- Sodium Sulphate, waterfree	7.500
- Sodium Chloride	2.691
- Potassium Chloride	1.015
Unit B	-
- Ascorbic Acid	4.700
- Sodium Ascorbate	5.900

Preparation of Movprep®

Dose Units A and B are dissolved in 1000 ml water.
The final preparation of the investigational product, Movprep® will be performed at the clinic.

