12 TRIAL CONDUCT

Table 4 Schedule of Events

Visit/Contact	0 Screening ^{a)}	1 CT-scan	2 Telephone interview and early termination ^{b)}
Day	-28 to -1	0	1-2
Visit window			12-48 hours
Subject information	X	X	
In/exclusion criteria		X	
Informed consent		X	
Pregnancy test ^{c)}			
Randomisation		X	
Subject demographics (incl. height and weight)		X	
Concomitant treatment		X	X
Concomitant illnesses		X	
Medical history		X	
Blood sample (clinical chemistry) ^{d)}		X	
Adverse event(s)		X	X
Dispensing of contrast agent		X	
Administration of Iodine contrast		X	
CT Scan		X	
Evaluation of contrast difference		X	
Evaluation of extension and distension composite score		X	
Evaluation of diagnostic ability		X	
Evaluation of contrast agent degradation		X	
Subject assessment of taste, smell, consistency etc.		X	
Compliance		X	

- a) No formal screening will be performed in the trial. However, since only one visit to the clinic is planned in this trial, all subjects will receive information regarding the trial prior to the clinic visit. Subjects will thus have time to consider participation and prepare questions, if needed.
- b) Also in case a subject is withdrawn after intake of the contrast agent the Early Termination form should be completed.
- c) Urine pregnancy test of all fertile females
- d) Blood sample (2 mL) will include Na, K, Ca, P in serum and will be taken prior to intake of contrast agents and post CT-scan.

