13 STATISTICAL METHODS

Before disclosure of randomisation codes, a separate statistical analysis plan (SAP) may be finalised, providing detailed methods for the analyses outlined below.

In general, data summaries will be stratified by the randomised treatment group (Lumentin® 44, diluted Omnipaque® and Movprep®). The randomisation is stratified by gender and this will be taken into consideration in the statistical analyses

Any deviations from the planned analyses will be described and justified in the final integrated trial report.

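### Serum Na, K, Ca and P are a named safety variable, but the plan gives them no change from baseline and no between-arm estimate with an interval

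*Combined protocol and SAP*

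**What the plan says.** The safety objective in section 6.2 is "To evaluate safety and tolerability after oral administration of each of three contrast agents". Section 7.2.3 lists among the safety variables "Safety laboratory evaluations (clinical chemistry"). Footnote d to the schedule of events in section 12 fixes the content and timing: "Blood sample (2 mL) will include Na, K, Ca, P in serum and will be taken prior to intake of contrast agents and post CT-scan".

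Section 13 has no subsection on laboratory values. Three general rules reach them:

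- Section 13.2: "Continuous data will be summarised using descriptive statistics (N, mean, median, standard deviation, minimum and maximum").
- Section 13, opening: "In general, data summaries will be stratified by the randomised treatment group".
- Section 13.1.3: "All safety analyses will be based upon the Safety Set".

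The more specific rules do not cover the values. Section 13.4.2 extends the primary method to secondary efficacy objectives only. Section 13.4.5 gives Fisher's exact tests for the three pairs of arms, but only for the adverse-event summary table. Section 10.5 sends new or worsening clinically significant laboratory findings to the adverse-event page, so those do reach the Fisher tests. Change from baseline, shift tables and between-arm differences are mentioned nowhere for the laboratory values.

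**The concern.** Between the two blood samples each subject drinks roughly a litre of oral agent and also receives IV iodine contrast, usually 60 to 115 mL, adjusted to body weight and kidney function (sections 7.1 and 9.7). The pre-to-post change within one arm is the sum of both, so it cannot be credited to the oral agent. Randomisation separates them: all arms receive the IV contrast, so a between-arm difference largely cancels its contribution. That difference is what the plan does not estimate.

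The question is not idle for this product. "Dibasic potassium phosphate" is a listed ingredient of Lumentin in Table 1 of section 9.1.1, and the three agents carry quite different mineral loads. What is at stake is how precisely a declared safety variable is reported. The primary endpoint is not touched.

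**Working it through.** **What the plan offers to check.** The documents give no figure for the laboratory values. The only power statement, 78% in section 13.6.1, concerns the primary variable. It reproduces: 1.50 / (2.00 × √(1/40 + 1/20)) = 2.739; 2.739 − 1.960 = 0.779; Φ(0.779) = 0.78. It has no bearing here beyond supplying the arm sizes, 40 and 20.

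**Mineral load per litre, from Tables 1 to 3 of section 9.1.** Assumptions: the 44% air in section 5.2 is by volume; the dispersion weighs 1 g/mL, so 1000 mL of foam holds 560 g; the potassium salt is anhydrous, as printed; minerals in the egg white powder are ignored.

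- Lumentin potassium: 0.63 g/100 g × 560 g = 3.53 g; / 174.18 g/mol = 20.25 mmol of salt; × 2 = 40.5 mmol K. Scaled by volume, this is 30 mmol at 750 mL, 32 at 800 mL and 49 at 1200 mL.
- Lumentin sodium: 0.19 g/100 g × 560 g = 1.06 g; / 156.01 = 6.8 mmol Na.
- Lumentin phosphate: 20.25 + 6.8 = 27 mmol.
- Movprep potassium: 1.015 / 74.55 = 13.6 mmol K.
- Movprep sodium: 2 × 7.500/142.04 + 2.691/58.44 + 5.900/198.11 = 105.6 + 46.0 + 29.8 = 181 mmol Na.
- Neither Movprep nor Omnipaque lists a phosphate salt, and Omnipaque lists no potassium salt.

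| mmol per litre as drunk | Lumentin foam | Movprep |
|---|---|---|
| K | 40.5 | 13.6 |
| Phosphate | 27 | none listed |
| Na | 6.8 | 181 |

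**Precision of a between-arm difference, Lumentin v one comparator.** The unadjusted 95% half-width for post-CT values is 1.96 × SD × √(1/40 + 1/20) = 0.537 × SD. Adjusting for the pre-intake value multiplies this by √(1 − r²), where r is the pre/post correlation: 0.8 at r = 0.6, and 0.6 at r = 0.8. The documents give neither SD nor r, so both are assumptions, shown over a range for serum K in mmol/L:

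| Assumed SD | Post values, unadjusted | Adjusted, r = 0.6 | Adjusted, r = 0.8 |
|---|---|---|---|
| 0.3 | 0.16 | 0.13 | 0.10 |
| 0.4 | 0.21 | 0.17 | 0.13 |
| 0.5 | 0.27 | 0.21 | 0.16 |

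Using t with 58 degrees of freedom instead of 1.96 moves the unadjusted figure at SD 0.4 only from 0.215 to 0.219.

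**What the planned tables can yield.** N, mean and SD of the post-CT values by arm are enough to compute the unadjusted column. They are not enough for the adjusted columns, or for an interval on the mean change, because separate pre and post SDs do not determine the SD of the change or the correlation.

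**The case against.** The case for leaving the plan alone has real substance.

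- *Laboratory problems already enter a comparison.* A reader might infer from the missing subsection that electrolytes are never compared between arms. Sections 10.2.1, 10.5 and 13.4.5 together show otherwise: clinically significant abnormal findings are adverse events and are compared by Fisher's test. They are pooled with all other events, however, and a systematic shift below clinical significance never gets there.
- *The by-arm columns are usable.* It is tempting to say that the trial cannot tell whether Lumentin shifts the electrolytes. The documents do not support that. The columns are randomised arms that all receive IV contrast, so a post-CT difference read across them is not confounded by it. What is lost is precision, and an interval on the change.
- *No comparison was promised.* The safety objective says evaluate, whereas the filling and palatability objectives say describe and compare. Description by arm is a defensible reading in phase II. That makes this an improvement to the plan, not a breach of it.
- *Other text could fill the gap.* The synopsis mentions Wilcoxon or Fisher tests in general terms, and section 13 allows a separate SAP. The synopsis sentence names no variable, and the SAP is optional.
- *The timing is less loose than it may look.* One might read the post sample as taken at any point between scan and departure. Section 7.1 describes the stay of at least 30 minutes first and the sample next, which suggests sampling near the end of the stay. It sets no window and does not say that the sample time is recorded.
- *More contrasts mean more chance findings.* Four analytes by two comparators is eight contrasts, and section 13.2 makes no multiplicity adjustment. This stands, and it argues for estimates rather than tests.

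**Conclusion.** The point holds as a worthwhile, inexpensive improvement. The plan collects paired electrolyte values in three randomised arms and then describes them by general rules that use neither the pairing nor the randomisation. A baseline-adjusted between-arm estimate would narrow the interval by 20% to 40% for r between 0.6 and 0.8; for potassium at an assumed SD of 0.4 mmol/L that is from about 0.21 to between 0.17 and 0.13 mmol/L. The relative gain depends on r alone; the absolute figures also depend on the SD and on 40 v 20 subjects. Those are evaluable numbers, and the Safety Set may be somewhat larger.

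Two further inferences should be resisted. First, potassium and phosphate are not simply where the agents differ most. They are where Lumentin delivers more than both comparators by listed ingredients; against Movprep the largest gap is sodium, about 175 mmol the other way (181 − 6.8). Second, an oral load is not a serum effect. The documents give no expected shift, and nothing here shows harm.

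**What to change.** Add a laboratory paragraph to section 13, on the Safety Set, for each of Na, K, Ca and P:

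1. Change from pre-intake to post-CT by arm (N, mean, SD, median, range).
2. Lumentin minus Omnipaque and Lumentin minus Movprep in the post-CT value, adjusted for the pre-intake value and gender (ANCOVA), each with a 95% CI. State that these are estimates and carry no significance claim.
3. Shift tables by arm against the laboratory's reference ranges.

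Record the clock time of the post-CT sample in the eCRF, so that differences in sampling time between arms can be seen.

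No extra subject, visit or blood sample is needed. The cost is one paragraph of analysis text, one eCRF field and eight more contrasts in the report. The contrasts are the one small downside, and presenting them as estimates limits it.

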13.3 Demographics, Baseline Characteristics and Concomitant Medications

Demographic data, baseline characteristics and concomitant medication will be summarised by means of descriptive statistics, stratified by treatment and randomisation stratification factors. Tables will be provided for the FA set and the PP set.

Concomitant medication will be presented by ATC classification.

13.4 Efficacy Analyses

The primary efficacy objective will be analysed using data from patients in both the FA set and the PP set considering the results from the PP set as the primary results.

13.4.1 Primary Efficacy Analysis

There are two primary objectives

- to compare the primary efficacy variable between patients randomised to Lumentin® 44 and patients randomised to diluted Omnipaque®
- to compare the primary efficacy variable between patients randomised to Lumentin® 44 and patients randomised to Movprep

The null-hypothesis that the primary efficacy variable is equal in the groups will be tested by means of the Wilcoxon rank sum test. In each of these analyses a two-sided p-value less than 5 % is considered statistically significant. A successful result is that both these tests are statistically significant and hence there is no need for multiplicity adjustment. The randomisation is stratified by gender but the statistical analysis of the primary objective will not be stratified.

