Statistical analyses	
The sample size estimation is based on a similar variable as the primary variable in this trial, i.e. the difference in contrast density in HU between bowel lumen and wall (mucosal lining), expressed as the mean of 9 measurement performed in the 5 selected sub-segments of the small bowel. At each measurement site, the equipment gives a mean value (given by the software of the X-ray equipment in Hounsfield Units) and a standard deviation (for the pixels in the Region of Interest, ROI). This mean value is from now on called “mean contrast density”.
 
In order to reach a 78 % probability (power) to detect (i.e. get a two-sided p-value less than 5 %) assuming a difference of 1.50 between the groups for the mean difference in contrast density and a standard deviation of 2.00 (assumptions based on an earlier trial, [1]) a total of 40 fully evaluable is needed in the Lumentin group and 20 in each of the comparator groups, i.e. a total of 80 fully evaluable subjects
 
The randomisation will be stratified by gender as the drinking capacity on average differs between males and females.
 
Descriptive statistics will be used to describe the results. When testing the hypotheses of equality between the groups p-values (two-sided) will be calculated by means of the Wilcoxon rank sum test or Fisher's exact test depending on the distribution of the variable of interest.

-----------------------------	---

1.1 Schedule of Events:

Visit/Contact	0 Screening ^{a)}	1 CT-scan	2 Telephone interview and early termination ^{b)}
Day	-28 to -1	0	1-2
Visit window			12-48 hours
Subject information	X	X	
In/exclusion criteria		X	
Informed consent		X	
Pregnancy test ^{c)}		X	
Randomisation		X	
Subject demographics (incl. height and weight)		X	
Concomitant treatment		X	X
Concomitant illnesses		X	
Medical history		X	
Blood sample (clinical chemistry) ^{d)}		X	
Adverse event(s)		X	X
Dispensing of contrast agent		X	
Administration of Iodine contrast		X	
CT Scan		X	
Evaluation of contrast difference		X	
Evaluation of extension and distension composite score		X	
Evaluation of diagnostic ability		X	
Evaluation of contrast agent degradation		X	
Subject assessment of taste, smell, consistency etc.		X	
Compliance		X	

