8.5 Subject Identification and Randomisation

Subjects referred to CT examination of the abdomen will receive an invitation to the CT examination by letter. An advertisement letter informing about the trial will be included in this referral letter.

All referrals for abdominal CT are read and prioritized by the investigator/sub-investigator. Those subjects, irrespective from which medical clinic, who the radiologist think are possible candidates for the trial, will have the advertisement letter added to the referral letter sent home to them with date and time for their CT-examination.

An invitation log will be kept with names of those receiving the advertisement letter. Subjects will subsequently be contacted by and asked if they are interested in participation. Those interested will be sent the subject information leaflet.

All subjects receiving the patient information leaflet will receive a screening number consisting of S followed by three digits: S-XXX starting with S-101.

The Investigator will allocate the screening numbers in ascending order.

Enrolled subjects who drop out of the trial before randomisation will retain their screening number.

Randomisation will occur at the clinic on the day of examination when all screening procedures have been performed and eligibility for the trial confirmed. Each randomised subject will receive a unique randomisation number consisting of R followed by three digits: R-XXX starting with R-101. Randomisation numbers will be allocated in strict ascending order according to a randomisation list

Randomised subjects who terminate their trial participation for any reason, regardless of whether trial drug was taken or not, will retain their randomisation number.

Subjects will be randomised on a 1:1:1 basis to Lumentin® 44, diluted Omnipaque® or Movprep®. The randomisation will be in blocks and stratified by gender as the drinking capacity differs between males and females.

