13.1 Trial Subjects

13.1.1 Disposition of Subjects

The number and percentage of subjects will be presented, stratified by treatment and overall, with sub-stratification by randomisation stratification factors.

Reasons for withdrawal will also be summarised.

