13.4.2 Secondary Efficacy Analysis

The secondary efficacy objectives will be analysed using the same principles and methods as the primary efficacy objectives.

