13.4.5 Adverse Events

AEs will be coded using the latest available version of the MedDRA, the version of which will be provided in the clinical trial report.

Pre-treatment AEs are AEs with onset prior to the intake of the contrast agent (Visit 1) that either stop prior to first administration of trial drug or are ongoing but do not deteriorate with respect to severity and/or relationship to trial drug after start of trial treatment. Pre-treatment AEs will be listed separately and will not be included in the AE tabulations. All other AEs will be considered as treatment-emergent AEs (TEAEs) and will be summarised per treatment group for the whole trial period.

An overall summary table will be provided showing the number and percentage of subjects with any:

- AE
- TEAE
- Severe TEAE

- Serious TEAE
- AEs leading to withdrawal
- Drug-related TEAE
- Drug-related severe TEAE
- Drug-related serious TEAE
- TEAE leading to withdrawal
- TEAE with outcome death

The two-sided p-values of Fisher's exact test for the 3 comparisons "Lumentin® 44 versus diluted Omnipaque®", "Lumentin® 44 versus p Movprep®" and "diluted Omnipaque® versus Movprep®" with regard to the percentages of subjects affected will be given in the overall summary table. The number of reported AEs will also be shown in this summary table.

The above summary table may be repeated, stratified by randomisation stratification factors.

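### Randomisation is stratified by gender, but the primary test (13.4.1) and apparently the secondary tests (13.4.2) ignore it: valid, but a gender-stratified rank test would be a cheap gain

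*Combined protocol and SAP*

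**What the plan says.** - **Design.** Section 8.5: "The randomisation will be in blocks and stratified by gender as the drinking capacity differs between males and females". The synopsis gives the same reason.
- **General rule.** Section 13, opening: "The randomisation is stratified by gender and this will be taken into consideration in the statistical analyses".
- **Primary test.** Section 13.4.1 specifies a Wilcoxon rank sum test of Lumentin 44 against each comparator, two-sided 5%, with success only if both are significant. It adds: "The randomisation is stratified by gender but the statistical analysis of the primary objective will not be stratified".
- **Secondary tests.** Section 13.4.2: "The secondary efficacy objectives will be analysed using the same principles and methods as the primary efficacy objectives". Stratification is not mentioned there, so that these tests are unstratified is an inference.
- **Where gender is used.** Only in summaries: disposition (13.1.1, "with sub-stratification by randomisation stratification factors"), demographics, baseline and concomitant medication (13.3, "stratified by treatment and randomisation stratification factors") and, optionally, adverse events (13.4.5, "The above summary table may be repeated, stratified by randomisation stratification factors").

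**The concern.** Stratifying the randomisation balances gender across arms. An analysis that ignores gender still leaves the between-gender variation in its error term, so it does not collect the precision that the balance bought. What is at stake is power, not false positives.

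The stated reason for stratifying bears most directly on secondary outcomes: extension, distension, fullness and ability to swallow. Section 7.1 allows Lumentin volumes from 750 to 1 200 mL, a ratio of 1200/750 = 1.6, so intake can vary even among subjects who meet the minimum.

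The route to the primary HU value is weaker. Section 10.1.1 leaves out segments that the agent did not reach. The per protocol set, which is primary under 13.1.3, by default excludes subjects below the minimum volume (13.1.2). Section 7.3.1 nevertheless says that filling is reflected in the primary variable.

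There is also a drafting gap. Section 13.4.1 settles the primary test. For the secondary tests, a statistician following the opening of section 13 could stratify, while one following 13.4.2 would not.

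**Working it through.** **1. The plan's own power figure (13.6.1).** Inputs: difference 1.50, SD 2.00, 40 vs 20 evaluable, two-sided 5%.

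- SE = 2.00 × √(1/40 + 1/20) = 0.5477
- 1.50 / 0.5477 = 2.739, and 2.739 − 1.960 = 0.779
- Power = Φ(0.779) = 78.2%, which matches the stated 78%. Under independence, 0.78 × 0.78 = 0.61, as stated.
- With the Wilcoxon efficiency √(3/π): 2.739 × 0.977 − 1.960 = 0.716, giving 76.3%. Simulation of the Wilcoxon test itself gives about 75%.

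**2. Why the unstratified test is conservative.** Let gender shift the outcome by g within-gender SDs in every arm, with half of each gender per arm.

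- The pooled SD is √(1 + g²/4) times the within-gender SD. Because the arms are balanced on gender, the difference between arms varies only with the within-gender SD.
- At g = 0.5: √1.0625 = 1.031, effective critical value 1.96 × 1.031 = 2.020, actual two-sided level about 4.3%.
- At g = 1.0: √1.25 = 1.118, critical value 2.191, level about 2.8%.
- Simulated levels at g = 0, 0.25, 0.5, 0.75 and 1.0 are 5.1, 4.9, 4.4, 3.7 and 2.8%. The stratified tests stay at 4.7 to 5.0%.

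**3. Power lost on the primary, shift common to all arms.** Simulated normal data, effect 1.50/2.00 = 0.75 SD, 40 vs 20, half of each gender, within-gender SD fixed at 2.00. The aligned rank test subtracts each gender's mean, ranks all subjects together, and uses the within-gender permutation variance.

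| Assumed gender shift (SD) | Unstratified | Van Elteren | Aligned rank | Aligned − unstratified |
|---|---|---|---|---|
| 0 | 75.0% | 73.3% | 74.6% | −0.4 |
| 0.25 | 74.4% | 73.3% | 74.5% | +0.1 |
| 0.5 | 72.7% | 73.2% | 74.3% | +1.6 |
| 0.75 | 69.8% | 73.1% | 74.4% | +4.6 |
| 1.0 | 66.0% | 73.1% | 74.3% | +8.3 |

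If the total SD is held at 2.00 instead, the gain per test runs from −0.3 (no shift) to +6.7 points (1.0 SD). With a 30:70 gender split it runs from −0.3 to +5.7. For the rule that both tests be significant (40/20/20 with a shared Lumentin arm), aligned minus unstratified is −0.4 to −0.6 points at no shift, about +2 at 0.5 SD and about +10 to +11 at 1.0 SD with half of each gender.

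**4. Secondary scores, shift common to all arms.** Within-gender SD fixed, effect 0.75 SD assumed. Unstratified against van Elteren:

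- Five-point item: 72.4 vs 72.1% at no shift, 69.7 vs 71.4% at 0.5 SD, 63.2 vs 71.3% at 1.0 SD.
- Filling sum score (10 to 90): 74.6 vs 74.1%, 72.5 vs 74.1% and 65.8 vs 73.9%.

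**5. Shift in the Lumentin arm only.** This is the pattern to expect if variable Lumentin volume is the mechanism.

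- Filling score, unstratified vs van Elteren: 73.0 vs 72.3% at 0.5 SD and 70.3 vs 69.2% at 1.0 SD. Aligned rank at 1.0 SD: 72.2%, a gain of 72.2 − 70.3 = 1.9 points.
- Five-point item, unstratified vs van Elteren: 70.0 vs 69.9% and 66.4 vs 66.6%.
- Normal data, aligned rank gain: 0.0 points at 0.5 SD and 1.6 at 1.0 SD.

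So van Elteren gains nothing here. The aligned rank test matches or beats the unstratified test from 0.25 SD up, within simulation error.

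**6. Larger HU differences.** At a true difference of 3 HU, every test has at least 99.9% power, and the choice does not matter.

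The gender shifts, gender mix, secondary effect size, item cut-points and reader correlation are assumptions. None is a figure from the documents.

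**The case against.** The best case for leaving the plan alone has four parts.

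- **The choice is explicit, prespecified and valid.** This stands. A reader might infer that ignoring the stratification factor invalidates the p-values or inflates false positives. It does not: the error is towards conservatism.
- **Section 13 is not contradicted.** A reader might see a flat conflict between its opening and 13.4.1. The wording there is loose enough to be met by the gender-stratified summaries, and the specific text governs the primary test. What remains is that the secondary handling is not stated. Section 13 says only that a separate SAP may be written, so the protocol may be the sole prespecification.
- **The primary is probably not at risk.** Section 5.2 describes density down to minus 600 HU, 7.3.1 reports a large lumen-to-wall difference in the earlier trial, and 10.1.1 describes the comparators as close to the wall, which is set at +80 HU. If the arms separate on anything like that scale, every rank test rejects. So a reader should not conclude that the trial stands to lose 10 points of joint power. That needs both the 1.50/2.00 assumption and a gender shift near 1.0 SD in all arms.
- **The mechanism may act in one arm only.** Comparator volumes follow departmental practice, so variable intake is mainly a Lumentin matter. Step 5 shows that this removes the case for van Elteren and most of the gain. It leaves the aligned rank test no worse than the unstratified one. Fullness at a fixed volume could still differ by gender in every arm, but no document figure gives a size.

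**Conclusion.** The point holds as a small efficiency and consistency improvement. It is not a validity error. Against the aligned rank test, the unstratified test loses:

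- under about 2 points per test for a common gender shift up to 0.5 SD, and about 7 to 8 points at 1.0 SD;
- about 0 at 0.5 SD and 1.5 to 2 points at 1.0 SD if gender acts only in the Lumentin arm;
- nothing that matters on the primary if the true HU difference is well above 1.50.

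These figures rest on 40:20:20 evaluable subjects. Section 8.5 also states 1:1:1. With about 28 per arm, the common-shift loss is similar: 2.1 points at 0.5 SD and 8.8 at 1.0 SD. The secondary endpoints have no planned power, and section 6.2 frames several as describe-and-compare aims. There the effect is on the sharpness of the comparison, not on trial success.

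**What to change.** 1. **Section 13.4.2 (main change).** State that the extension, distension and diagnostic ability scores and the five drinkability items are compared with one gender-stratified aligned rank test, tie-corrected.
2. **Section 13.4.1.** Use the same test as primary, with the unstratified Wilcoxon as sensitivity analysis. If the unstratified primary is kept, add the aligned rank test as the one prespecified sensitivity analysis.
3. **Section 13, opening.** Replace the general statement with a list of the analyses that use gender.

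Van Elteren is not recommended. With no gender effect it costs about 1.5 points per primary test and 2.0 joint (59.6 to 57.6%), and it gains nothing if gender acts in one arm only.

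**Cost.** One sentence in each of three sections and a few lines of code. If gender has no effect, the aligned rank test gives up about 0.5 point or less per test, and about 0.5 point of joint power (59.6 to 59.2% with total SD fixed).
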